Our eligibility criteria for the study is limited to males in an effort to reduce variability within our small sample size due to the known gender differences in the physiological response to hypoglycemia both acutely (22, 23), as well as during a 72-hr fast (24). Previous studies have demonstrated a reduced release of counterregulatory hormones (e.g. epinephrine and glucagon) in response to hypoglycemia in women. Given that this is a pilot study with a limited number of participants to be studied, we have chosen to minimize the potential variability in our outcome measures caused by these gender differences, by limiting our enrollment to males. This will allow us to minimize our participant numbers.

Number of Subjects

Up to ten subjects will be enrolled in this study.

Recruitment Methods

Standard recruitment methods (email, print, social media advertisements, etc.) will be used to identify potential participants. As this is a study requiring consecutive overnight stays at the Inpatient Unit at Pennington Biomedical, the PI may submit a privacy board request identifying potentially eligible participants who have previously completed extended-stay studies at Pennington Biomedical and have consented to future contact.

Study Timelines

A participant's duration of study participation will be approximately 4 days.

The estimated duration to enroll all study subjects is anticipated to be nine months.

The estimated duration to complete the study (primary analyses) is 1 year (April 2016)

Study Endpoints

Primary endpoints:

- Percent ^{13}C enrichment of cerebral glutamine, glutamate, and bicarbonate, as measured by magnetic resonance spectroscopy (MRS)
- Glial acetate oxidation rate and astroglial TCA cycle rate ascertained through mathematical modeling of MRS data

Secondary endpoints:

- Change in glucose levels
- Change in leptin levels

Procedures Involved

The study design and schedule of assessments are depicted in **Figure 1** and **Table 1**.

Measurement	Screening Visit	Observational Study Visit			
		Day 0	Day 1	Day 2	Day 3
Height	X				
Weight	X	X	X	X	X
Medical History	X				
Physical exam	X				X
Blood collection		X	X	X	X
Blood collection for future use**	X	X	X	X	X
Urine collection	X	X	X	X	X
Blood glucose*	X				X
ECG	X				
CGM		X	X	X	X
Vital signs	X	X	X	X	X
¹³ C - MRS†		X			X
DXA		X			
Adverse events			X	X	X

*via finger-stick.
 **Optional
 †IV procedure and serial blood collection
 CGM: Continuous glucose monitoring

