Participants will complete a screening visit, and a 4-day observational inpatient stay.

Screening:

[figure not shown]
Participants will complete a screening visit at the Pennington Biomedical Outpatient Clinic to assess eligibility. After providing written informed consent, the following procedures will be completed: anthropometrics, vital signs, 10ml blood draw for future use (optional), fasting glucose by finger stick, urine collection to measure ketonuria, ECG, and medical history and physical examination by a physician or nurse practitioner.

4-Day Observational Inpatient Stay:

Eligible subjects will be scheduled for the observational study visit (OSV) which lasts for approximately 80 continuous hours. The OSV begins (Day -1) with provision of a standard lunch and supper (Standard American Diet) to be consumed the day prior to the fast. Subjects will be instructed to eat only the food provided for lunch and supper, and arrive at the inpatient unit the following morning after at least a 10 hour overnight fast.

On Day 0, subjects will be weighed, vital signs and body composition (DXA) will be measured, and blood (4mL) and urine will be collected for baseline measurements of serum hormones, glucose, and ketones, as well as ketonuria. Blood (10 mL) will also be collected for future use if the participant provides permission. Baseline glial metabolism will be measured via MRS utilizing a simultaneous intravenous infusion of ¹³C labeled acetate. ¹³C-acetate will be administered for the first hour of the MRS procedure, at a rate of 6 mg/ kg per min for the first 5 minutes, and 3 mg/kg per min for the remainder.

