Following the MRS scan, subjects will be provided a standard breakfast, and then will begin ~3 days and 3 hours of fasting. During the fast, subjects will be allowed to drink water ad libitum and to perform normal ambulatory activity, excluding exercise. A subcutaneous continuous glucose monitoring system will be utilized to track glycemia during the first 72 hours of the fast. After approximately 24, 48, and 72 hours of the initiation of the fast, blood (10mL for study use and 10mL for future use if the participant provides permission) and urine will be collected, weight and vital signs measured, and adverse events recorded. At 72 hours of the fast, measurement of glial metabolism will be repeated via MRS. Subjects will then be provided breakfast (Standard American Diet, overfed by 50%) and discharged from the Inpatient Unit after an end of study evaluation (physical, blood glucose) by the Medical Investigator.

Study Procedure Descriptions

- **Acetate infusion/MRS procedure:** Glial metabolism will be measured via MRS utilizing a simultaneous intravenous infusion of ¹³C labeled acetate. An intravenous catheter will be placed in a vein of each arm, one to infuse ¹³C-acetate and the other to draw blood samples.
 - Participant alignment and baseline scans: 30 to 40 minutes prior to the start of acetate infusion, participants will be placed in the MRI scanner to conduct both preliminary alignment via MRI as well as baseline MRS scans.
 - Acetate infusion protocol: The infusate, 350 mM [1-¹³C] acetate (99% enriched; Microbiological/Pyrogen tested), will be prepared by the PBRC Pharmacy. ¹³C-acetate will be administered for the first hour of the MRS procedure, at a rate of 6 mg/kg per minute for the first 5 minutes, and 3 mg/kg per minute for the remainder.

- Blood sampling protocol: Venous blood samples (approximately 2 mL each) will be obtained about every 10 minutes, starting 20 minutes before the beginning of the acetate infusion, and will be continued throughout the infusion (~15 total draws).
- MRS protocol: During IV infusion of [1-13C] acetate, MRS spectra will be collected every 10 minutes for 120 minutes using a 3 Tesla GE SIGNA MRI scanner housed in the PBRC Biomedical Imaging Center.

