- Intravenous ¹³C Acetate infusion: There is the possibility of pain and bruising at the vein where the needle associated with the IV line is inserted. Aseptic (sterile) technique and trained nursing staff minimizes these risks. We have significant experience in preparing and administering sterile solutions intravenously. All solution will be prepared by a licensed pharmacist. ¹³C is a naturally occurring stable isotope of carbon which is commonly use in clinical research studies. There are no reported risks associated with administration of ¹³C labeled compounds. The amount of acetate infused relative to blood volume is very low and therefore plasma pH is not anticipated to be affected.
- Urine collection: There is no risk to participants in collecting their urine.

Potential Benefits to Subjects

There is no direct benefit to participants.

Sharing of Results with Subjects

Results will not be shared with subjects.

Setting

This study will be conducted at Pennington Biomedical Research Center in the Outpatient Unit, Inpatient Unit and Bioimaging facility. Measurement of 1-¹³C acetate levels and ¹²C acetate levels will be completed by the Biological and Small Molecule Mass Spectrometry Core of the Department of Chemistry at the University of Tennessee-Knoxville through a contractual agreement.

Resources Available

Pennington Biomedical Outpatient and Inpatient staff are highly trained individuals with a breadth of experience in clinical research. All have completed human subjects protection training and highly knowledge of local study site and culture. A physician is

on-call 24 hours a day and is available for consultation or evaluations if necessary. The study regulatory documents will be provided to all staff involved and a startup meeting will be held to ensure all persons assisting with the research are adequately informed about the protocol, the research procedures, and their duties and functions.

Measurement of 1-¹³C acetate levels and ¹²C acetate levels will be completed by the Biological and Small Molecule Mass Spectrometry Core of the Department of Chemistry at the University of Tennessee-Knoxville through a contractual agreement. Specimens will be collected, prepared, processed, labeled, stored, and shipped by the PBRC Clinical Chemistry Lab.

Compensation

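### At the protocol's own rate and concentration, each one-hour acetate infusion is about 6–13% of an assumed blood volume, so the risk section's premise of a very low amount, and the pH expectation resting on it, are unsupported

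*Combined protocol and SAP*

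**What the plan says.** Under Risks to Subjects, the item on the intravenous ¹³C acetate infusion states: "The amount of acetate infused relative to blood volume is very low and therefore plasma pH is not anticipated to be affected". No total dose, infused volume, calculation or reference accompanies it.

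The dose is set out twice, in the Day 0 text of the 4-Day Observational Inpatient Stay and under Study Procedure Descriptions, and the two agree: "at a rate of 6 mg/kg per minute for the first 5 minutes, and 3 mg/kg per minute for the remainder". The second of these adds the concentration: "The infusate, 350 mM [1-¹³C] acetate (99% enriched; Microbiological/Pyrogen tested), will be prepared by the PBRC Pharmacy". On duration it says "¹³C-acetate will be administered for the first hour of the MRS procedure". The MRS protocol item in the same list says "During IV infusion of [1-13C] acetate, MRS spectra will be collected every 10 minutes for 120 minutes", and the blood sampling item says that draws every 10 minutes or so, starting 20 minutes before the infusion, "will be continued throughout the infusion (~15 total draws".

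The procedure is done on Day 0 and repeated at 72 hours of fasting. Under Blood collection (study use), scan blood is assayed for plasma acetate concentration and ¹³C enrichment. The daily samples cover a list of hormones and metabolites, given as examples, that names no pH, bicarbonate or electrolytes.

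**The concern.** The risk statement has two parts joined by a *therefore*. The amount is very low relative to blood volume, and for that reason no effect on plasma pH is expected. The first part can be checked against the protocol's own rate and concentration, and a rough check suggests an infused volume of several hundred millilitres in an hour for an adult man. If the first part fails, the second has no other support in the documents.

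This is the risk section's only statement on the metabolic effect of the infusion, in a study that offers participants no direct benefit. No specified measurement would show whether the expectation was met at either scan. The second scan follows three days without food, when the protocol itself is tracking ketones in blood and urine.

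**Working it through.** The plan gives no figure for the load, so there is none to reproduce. The check builds it from the stated inputs.

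**Inputs from the protocol:** 6 mg/kg/min for 5 min, then 3 mg/kg/min; one hour in total; 350 mmol/L.

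**Assumptions, not in the documents:** molar mass by form of the ¹³C-labelled compound (trihydrate 137.07, anhydrous sodium salt 83.03, acetate ion 60.04 g/mol); blood volume 70 mL/kg, with 65–80 mL/kg as the range.

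**Step 1, dose per session.** 6 × 5 + 3 × 55 = 30 + 165 = 195 mg/kg.

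**Step 2, amount and volume.** mmol/kg = 195 ÷ molar mass; mL/kg = (mmol/kg) ÷ 0.350; share of blood volume = (mL/kg) ÷ 70.

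| mg refer to | mmol/kg | mL/kg | % of blood volume at 70 mL/kg | % at 80 to 65 mL/kg |
|---|---|---|---|---|
| sodium acetate trihydrate | 195/137.07 = 1.42 | 4.1 | 5.8 | 5.1–6.3 |
| anhydrous sodium acetate | 195/83.03 = 2.35 | 6.7 | 9.6 | 8.4–10.3 |
| acetate ion | 195/60.04 = 3.25 | 9.3 | 13.3 | 11.6–14.3 |

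No body weight is needed for these ratios.

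**Step 3, totals for illustration.** The documents give no weight. At an assumed 75 kg the dose is 195 × 75 = 14.6 g: 107 mmol in 0.31 L (trihydrate), 176 mmol in 0.50 L (anhydrous) or 244 mmol in 0.70 L (ion). The BMI criterion of 20.0–27.9 with an assumed height of 1.65–1.90 m allows about 54–101 kg. Across that range and all three forms the totals run from 77 to 328 mmol and from 0.22 to 0.94 L.

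**Step 4, duration.** Fifteen draws at 10-minute intervals from −20 min end at −20 + 14 × 10 = +120 min. Draws from −20 to +60 min would number only nine. The draw count and the MRS item therefore both point to 120 minutes, against the stated first hour. At 120 minutes the dose would be 6 × 5 + 3 × 115 = 375 mg/kg. That is 2.74, 4.52 or 6.25 mmol/kg in 7.8, 12.9 or 17.9 mL/kg for the three forms, or 11%, 18% or 26% of blood volume at 70 mL/kg.

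**The case against.** The strongest reply is that nothing here shows a pH effect. The protocol says only that none is expected, not that none can occur. The figures are loads before any clearance, and buffering, ventilation and excretion are left out. The documents contain no pH data. All of that stands. A reader might infer that the protocol's figures prove plasma pH will shift, or might compare the load with an assumed body bicarbonate pool to suggest a large disturbance. The documents support neither. The figures undercut the premise about amount, and so the stated reason for the expectation; they do not establish its opposite.

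Second, totals in millimoles and litres depend on a weight and a salt form that the documents omit. This also stands, which is why the result rests on per-kilogram figures for all three forms. The smallest of them is still about 6% of blood volume.

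Third, a reader might infer that the bicarbonate endpoint is biased. The Study Endpoints section lists as primary "Percent ^{13}C enrichment of cerebral glutamine, glutamate, and bicarbonate, as measured by magnetic resonance spectroscopy (MRS"), and acid-base state may differ between a fed-state baseline and a 72-hour fast. But the endpoint is percent enrichment in brain, not plasma concentration. The weight-based regimen is the same at both scans, so the added load is largely common to the comparison. The size of any baseline difference is unknown. The Power analysis section, moreover, names only glutamine and glutamate as primary outcomes. Confounding is possible but not shown.

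Fourth, the risk sentence is not offered as a reason for omitting acid-base tests, and the daily analyte list is open-ended. The supportable statement is that no such measurement is specified.

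**Conclusion.** The point holds as an unsupported safety statement that sits against the protocol's own dosing figures. Taking the one-hour duration, each session delivers 195 mg/kg in a volume of about 6–13% of an assumed 70 mL/kg blood volume (5–14% over 65–80 mL/kg), depending on a salt form that is not stated. That is hard to describe as very low, and the pH expectation loses the only reason given for it. Whether pH changes is left open.

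The duration text adds a separate inconsistency, which would raise the dose to 375 mg/kg if the infusion ran as long as the spectra. The percentages rest on the assumed molar masses and blood volume; the 195 and 375 mg/kg do not. The risk wording should be corrected before it is relied on.

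**What to change.** 1. State the form to which mg/kg refers, and give mmol/kg and mL/kg per session.
2. Reconcile the first-hour infusion with the 120 minutes of spectra and the 15 or so draws said to span the infusion. Reconcile both dose descriptions with the risk statement.
3. Support the statement on amount and pH with evidence, or revise it.
4. Specify bicarbonate or pH measurement before and at the end of infusion at both scans, using draws already planned. Whether the 2 mL samples intended for mass spectrometry can be handled for this needs checking with the laboratory.
5. Report the pre-infusion values beside the bicarbonate-enrichment results, as context and not as an adjustment.

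The cost is a protocol wording change, a small assay cost (two readings per scan) and a less favourable risk statement. No dose, duration or clinical rule is proposed; those are for the sponsor to settle.
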